2.4.5.1 Analyses of adverse events

Generalities

The primary focus of adverse event reporting will be on treatment-emergent adverse events (TEAEs) in the open-label period. Posttreatment adverse events will be described separately.

TEAEs will be further differentiated as "TEAEs during treatment epoch" and "TEAEs during accelerated elimination epoch". TEAEs during treatment epoch and TEAEs during accelerated elimination epoch will be analyzed separately and combined, as applicable.

If an adverse event date/time of onset (occurrence, worsening, or becoming serious) is incomplete, an imputation algorithm will be used to classify the adverse event as treatment-emergent, or posttreatment. The algorithm for imputing date/time of onset will be conservative and will classify an adverse event as treatment emergent unless there is definitive information to determine it is posttreatment. Details on classification of adverse events with missing or partial onset dates are provided in [Section 2.5.2](#).

Adverse event incidence tables will present by SOC, HLG, HLT, and PT, sorted in alphabetical order for each treatment group, the number (n) and percentage (%) of patients experiencing an adverse event. Multiple occurrences of the same event in the same patient will be counted only once in the tables within a treatment period. The denominator for computation of percentages is the safety population within each treatment group.

Sorting within tables ensures the same presentation for the set of all adverse events within the observation period (treatment-emergent, and posttreatment). For that purpose, the table of all treatment-emergent adverse events presented by SOC and PT sorted by the internationally agreed SOC order and decreasing frequency of PTs within SOCs will define the presentation order for all other tables unless otherwise specified. Sorting will be based on results for the overall treatment group.

Analysis of all treatment-emergent adverse events

The following treatment-emergent adverse event summaries will be generated for the safety population.

- Overview of treatment-emergent adverse events, summarizing number (%) of patients with any
 - Treatment-emergent adverse event
 - Serious treatment-emergent adverse event
 - Treatment-emergent adverse event leading to death
 - Treatment-emergent adverse event leading to permanent treatment discontinuation
- All treatment-emergent adverse event by primary SOC, HLG, HLT, and PT, showing number (%) of patients with at least 1 treatment-emergent adverse event sorted by the SOC internationally agreed order. The other levels (HLG, HLT, PT) will be presented in alphabetical order.

- All treatment-emergent adverse events by primary SOC and PT, showing the number (%) of patients with at least 1 treatment-emergent adverse event, sorted by the internationally agreed SOC order and by decreasing incidence of PTs within each SOC. This sorting order will be applied to all other tables, unless otherwise specified.
- Common TEAEs (incidence $\geq 2\%$ in any treatment group for PT) by primary SOC, HLGT, HLT, and PT, showing number (%) of patients with at least one common TEAE, sorted by the internationally agreed SOC order. The other levels (HLGT, HLT, and PT) will be presented in alphabetical order.
- All treatment-emergent adverse events regardless of relationship and related by primary SOC, HLGT, HLT and PT, showing the number (%) of patients with at least 1 treatment-emergent adverse event, sorted by the internationally agreed SOC order. The other levels (HLGT, HLT, PT) will be presented in alphabetical order.
- All treatment-emergent adverse events by maximal severity, presented by primary SOC and PT, showing the number (%) of patients with at least 1 treatment-emergent adverse event by severity (ie, mild, moderate, or severe), sorted by the sorting order defined above.
- Number (%) of patients experiencing treatment-emergent adverse event(s) presented by primary and secondary SOC, HLGT, HLT, and PT sorted by the internationally agreed SOC order. The other levels (HLGT, HLT, PT) will be presented in alphabetical order
- Number (%) of patients experiencing TEAE(s) presented by PT, sorted by decreasing incidence of PT.
- By patient listing of TEAE(s) occurred within 2 months after first dose increase for teriflunomide treated patients showing treatment group, patient identified, age, gender, race, primary SOC decode, PT decode, verbatim (diagnosis), onset date and study day, date of death (if relevant), recovery date/time, event duration, outcome, intensity/grade, relationship to study treatment, action taken with study treatment and corrective treatment/therapy, AE serious criteria, flag for AE status, and Covid-19 related flag.

Analysis of all treatment emergent serious adverse event(s)

- All treatment-emergent serious adverse events by primary SOC, HLGT, HLT, and PT, showing the number (%) of patients with at least 1 serious treatment-emergent adverse event, sorted by the internationally agreed SOC order. The other levels (HLGT, HLT, PT) will be presented in alphabetical order.
- All treatment-emergent serious adverse events by primary SOC and PT, showing the number (%) of patients with at least 1 serious treatment-emergent adverse event, sorted by the internationally agreed SOC order and by decreasing incidence of PTs within each SOC.
- All treatment-emergent serious adverse events regardless of relationship and related to IMP, by primary SOC, HLGT, HLT, and PT, showing the number (%) of patients with at least 1 treatment-emergent serious adverse event, sorted by the internationally agreed SOC order. The other levels (HLGT, HLT, PT) will be presented in alphabetical order.

- Number (%) of patients with at least one treatment-emergent serious adverse events by seriousness criteria.
- By-patient listing of treatment-emergent SAEs showing treatment group, patient identified, age, gender, race, primary SOC decode, PT decode, verbatim (diagnosis), onset date and study day, date of death (if relevant), recovery date/time, event duration, outcome, intensity/grade, relationship to study treatment, action taken with study treatment and corrective treatment/therapy, AE serious criteria, flag for AE status, and Covid-19 related flag.

Analysis of all treatment-emergent adverse event(s) leading to treatment discontinuation

- All treatment-emergent adverse events leading to treatment discontinuation, by primary SOC, HLGT, HLT, and PT, showing the number (%) of patients sorted by the internationally agreed SOC order. The other levels (HLGT, HLT, PT) will be presented in alphabetical order.
- All treatment-emergent adverse events leading to treatment discontinuation, by primary SOC and PT, showing the number (%) of patients sorted by the internationally agreed SOC order and by decreasing incidence of PTs within each SOC.
- By-patient listing of TEAEs leading to treatment discontinuation showing treatment group, patient identified, age, gender, race, primary SOC decode, PT decode, verbatim (diagnosis), onset date and study day, date of death (if relevant), recovery date/time, event duration, outcome, intensity/grade, relationship to study treatment, action taken with study treatment and corrective treatment/therapy, AE serious criteria, flag for AE status, flag for seriousness, and Covid-19 related flag.

AESIs summaries

- All treatment emergent adverse events of special interest, by primary SOC, HLGT, HLT, and PT, showing number (%) of patients with at least one TEAE sorted by SOC internationally agreed order. The other level (HLGT, HLT, PT) will be presented in an alphabetic order.

In addition, the following exposure adjusted analyses will be performed for treatment emergent adverse events with pre-specified monitoring adverse events.

The frequency of TEAEs across pre-defined time intervals will be provided for the treatment emergent AESIs, where the time intervals will be defined as: $>0 \leq 1$ week, $>1 \leq 4$ week, $>4 \leq 12$ weeks, $>12 \leq 24$ weeks, $>24 \leq 36$ weeks, $>36 \leq 48$ weeks, $>48 \leq 60$ weeks, $>60 \leq 72$ weeks, $>72 \leq 84$ weeks, $>84 \leq 96$ weeks, $>96 \leq 108$ weeks, $>108 \leq 120$ weeks, $>120 \leq 132$ weeks, $>132 \leq 144$ weeks, $>144 \leq 156$ weeks, $>156 \leq 168$ weeks, $>168 \leq 180$ weeks, $>180 \leq 192$ weeks and >192 weeks for open-label period. In each time interval, the denominator for calculation of percentage will be the number of patients exposed at the beginning of the time interval who did not report the given TEAE in the preceding intervals and the numerator will be the number of patients with at least one TEAE occurring in this time interval. Only the first event will be counted and all recurrent events will not be included.

Analysis of posttreatment adverse events

- All posttreatment adverse events by primary SOC and PT, showing the number (%) of patients with at least 1 posttreatment adverse event, sorted by the internationally agreed SOC order and decreasing incidence of PTs within each SOC.
- All posttreatment serious adverse events by primary SOC and PT, showing the number (%) of patients with at least 1 posttreatment serious adverse event, sorted by the internationally agreed SOC order and decreasing incidence of PTs within each SOC.

Long-term Safety Analysis

Long-term safety of teriflunomide exposure will also be analyzed by including all teriflunomide exposure, ie, from randomization in the double-blind period in the teriflunomide group and from start in the open-label period in the placebo group, for the complete study population analyzed in one overall group. Key safety analyses on TEAEs, SAEs, TEAEs leading to treatment discontinuation and AESIs.

Safety Subgroup Analysis

Safety subgroup analyses will be performed for key tables of TEAEs/SAEs/AESIs and TEAEs leading to treatment discontinuation during the treatment-emergent adverse event period in the open-label period by:

- Intrinsic factors
 - Age group at study consent of the double-blind period (<13, ≥13 years)
 - Gender
 - Race
 - Pubertal status (at study consent, and at disease onset)
 - Baseline weight group in the double-blind period (≤40, >40 kgs)
 - MS subtypes (relapsing-remitting MS, other forms)
 - High disease activity at baseline (defined as 2 or more relapses in the past year of screening, and 1 or more Gadolinium enhancing lesions on baseline MRI of the double-blind period) (Yes, No)
- Extrinsic factors
 - Region (as defined in [Section 2.5.5](#)).

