## 5 STUDY DESIGN

### 5.1 DESCRIPTION OF THE PROTOCOL

EFC11759 is a multicenter, randomized, double-blind, placebo-controlled, parallel-group study. It consists of:

- A screening period up to 4 weeks, designed to evaluate suitability to participate in the trial, in terms of MS diagnosis, MS treatment(s), and safety screening evaluations. No investigational medicinal product (IMP) is administered in this period.
- A double-blind treatment period of up to 96 weeks total duration for each patient
  - Patients are randomized to either teriflunomide or placebo at 2:1 ratio (110 patients on teriflunomide vs. 55 patients on placebo),
  - It includes a blinded PK run-in (8 weeks) phase consisting of 4 weeks of PK sample collection plus 4 weeks of analysis (corresponding to the first 8 weeks after randomization). The PK run-in (8 weeks) phase is intended to provide individual PK parameters to allow the dose adjustment to the 14mg adult-equivalent dose for the rest of the study from Week 8,
  - Patients experiencing a relapse after the PK run-in (8 weeks) and if confirmed by the Relapse Adjudication Panel (RAP) will have the option to continue in an open label period. If RAP does not confirm the relapse, the patient can continue in the double-blind phase or prematurely discontinue the treatment. Similarly, patients with high MRI activity (defined in [Section 8.1](#)) or completing the 96-week double-blind period will have the option to continue in the open label period.
- An open-label period for the remainder of 192 weeks after randomization

The open-label period will follow the double-blind period and last until 192 weeks after randomization. Its duration for a given patient will depend on when the patient enters this period. The duration of the open-label period will be 96 weeks for patients completing the 96-week double-blind period on treatment, and longer for patients switching to open-label during the initial 96 week double-blind period at the occurrence of a confirmed relapse or in case of high MRI activity.

It includes a blinded PK run-in phase (8 weeks, similarly to the double-blind period).

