2.4.5 Analyses of safety data

The summary of safety results will be presented by treatment patients actually received in the double-blind and open-label period (placebo/teriflunomide and teriflunomide/teriflunomide) and overall treatment group. Baseline values of the double-blind period will be used as the baseline in the safety analysis for the open-label CSR, unless otherwise noted.

General common rules

All safety analyses will be performed on the safety population as defined in [Section 2.3.3](#), unless otherwise specified, using the following common rules:

- Safety data in patients who do not belong to the safety population will be listed separately.
- The baseline value is defined as the last available value before the first intake of IMP in the double-blind period.
- The potentially clinically significant abnormality (PCSA) values are defined as abnormal values considered medically important by the Sponsor according to predefined criteria/thresholds based on literature review and defined by the Sponsor for clinical laboratory tests, vital signs, and ECG (PCSA version dated May 2014 [[Appendix A](#)]).
- PCSA criteria will determine which patients had at least 1 PCSA during the treatment-emergent adverse event period, taking into account all evaluations performed during the treatment-emergent adverse event period, including nonscheduled or repeated evaluations. The number of all such patients will be the numerator for the on-treatment PCSA percentage.
- The treatment-emergent PCSA denominator by group for a given parameter will be based on the number of patients assessed for that given parameter in the treatment-emergent adverse event period by treatment group on the safety population.
- For quantitative safety parameters based on central laboratory/reading measurements, descriptive statistics will be used to summarize results and change from baseline values of the double-blind period by visit and treatment group. Summaries will include the endpoint value and/or the minimum and maximum value. The endpoint value is commonly defined as the value collected at the same day/time of the last administration of IMP in the open-label period. If this value is missing, this endpoint value will be the closest value prior to the last dose intake.

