- j* The following safety laboratory tests will be conducted in between clinical routine lab at Weeks 8, 16, 20, 30 and then every 12 weeks up to the end of treatment (EOT). Study nurse visit at patient's home can be provided (except at Week 8). In addition at EOT+2 weeks and EOT+4 weeks. The following safety laboratory testing will be conducted: (measuring hematology and differential panel [as above], liver function tests [ALT, AST, GGT, total bilirubin, and direct/indirect bilirubin] and pancreatic enzymes [serum amylase and lipase]). In addition, uric acid and inorganic phosphorus will be done at EOT+2 weeks and EOT+4 weeks.
- k* PK samples will be collected at Week 2, 3, and 4 (PK run-in (8 weeks) period); an additional 4th sample may be required in case of inadequate sampling or information/variability from 3 samples. Study nurse visit at patient's home can be provided when PK sampling is not synchronized with routine lab visit (W2, W3 or in the event the 4th sample is needed).
- l* Post drug elimination procedure: samples to be collected for verification of plasma teriflunomide concentrations ≤ 0.02 $\mu\text{g/mL}$.
- m* In addition if a patient has a vaccination, antibody titers will be assessed before and after vaccination (inactivated vaccines only)
- n* EDSS required also after each clinical relapse, to be performed within 7 days.
- o* If patient is treated with steroids the MRI should be performed after 14 days discontinuation of the steroids.
- p* ECG should be performed only for patients who had new abnormalities on the EOT ECG.
- q* Cognitive Battery Tests: TMT-A and B, SRT, Beery VMI, BVMTR, D-KEFS Fluencies (Letter and Category); BVMTR and WASI Vocabulary potentially supplemental. When available.
- r* The number of visits is linked to the time in the previous double blind phase as the maximum period in the study is 192 weeks. The maximum potential duration is therefore 184 weeks.
- s* The date of the menarche should be captured if applicable.
- t* IVRS only if treatment is stopped.
- u* An optional additional extension period with teriflunomide is offered to young patients, to provide them treatment until they are 18 years old and/or can switch to commercial product, whichever comes first.

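### Open-label TEAE, SAE and discontinuation tables give crude percentages by former arm, although former placebo patients are expected to have modestly longer planned open-label exposure

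*SAP*

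**What the plan says.** **Grouping and denominator.** SAP 2.4.5 presents safety results "by treatment patients actually received in the double-blind and open-label period (placebo/teriflunomide and teriflunomide/teriflunomide"), with an overall column. For incidence tables, SAP 2.4.5.1 adds: "The denominator for computation of percentages is the safety population within each treatment group". The listed outputs for all TEAEs, common TEAEs, SAEs and TEAEs leading to discontinuation are numbers and percentages of patients. None names a person-time rate.

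**Planned open-label time.** Protocol 5.1: "The duration of the open-label period will be 96 weeks for patients completing the 96-week double-blind period on treatment". The same section makes it "longer for patients switching to open-label during the initial 96 week double-blind period at the occurrence of a confirmed relapse" or high MRI activity. SAP Appendix C gives the upper limit: "The maximum potential duration is therefore 184 weeks".

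**Where time at risk is already used.**
- SAP 2.4.5.1, under AESIs: "the following exposure adjusted analyses will be performed for treatment emergent adverse events with pre-specified monitoring adverse events". The method described there counts first events per time interval, over patients still exposed at the start of the interval who have not yet reported the event.
- SAP 2.2 plans Kaplan-Meier estimates for permanent discontinuation for any reason.
- SAP 2.4.3.1 tabulates open-label exposure by group, as a continuous variable and in categories up to 192 weeks.
- SAP 2.4.5.3 shows key laboratory abnormalities by duration of exposure and plans Kaplan-Meier estimates for ALT and bilirubin elevations.

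**Intent.** SAP 2.4.5 describes the safety analysis as essentially descriptive, with no systematic testing.

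**The concern.** A crude percentage answers how many patients had the event during whatever time they were observed. Two columns of such percentages compare fairly only if observation time is similar. Here its length is tied to the randomized arm: a confirmed relapse after the PK run-in moves a patient early into the open-label period and so lengthens it, and relapse is the endpoint on which the trial expects the arms to differ.

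The direction is predictable. If teriflunomide reduces relapses, more former placebo patients switch early, and patients newly started on teriflunomide tend to look slightly worse than those already treated, even at equal rates. The separate exposure table shows that an imbalance exists, but it does not let a reader correct an individual SAE or preferred-term row.

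**Working it through.** **1. Reproduce the plan's inputs (SAP 1.3, Protocol 11.1).** Placebo hazard: -ln(0.40)/2 = 0.4581 per year. At hazard ratio 0.5: 0.2291. Teriflunomide 2-year risk: 1 - exp(-2 × 0.2291) = 36.8%. All match. An exponential-survival sample size with 2:1 allocation and 20% dropout over 2 years gives 167.5, close to the planned 165.

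**2. Share of open-label entrants who switched early.** Dropout hazard: -ln(0.80)/2 = 0.1116 per year. Switching is possible from Week 8 to Week 96, that is 88/52.18 = 1.6865 years. Let k be the sum of relapse and dropout hazards.
- Placebo: k = 0.5697. Complete: exp(-0.5697 × 1.6865) = 0.3826. Switch: (0.4581/0.5697) × 0.6174 = 0.4965. Early share: 0.4965/(0.4965 + 0.3826) = 56%.
- Teriflunomide: k = 0.3406. Complete: 0.5630. Switch: (0.2291/0.3406) × 0.4370 = 0.2939. Early share: 0.2939/0.8569 = 34%.

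Dropout in the first 8 weeks leaves a factor exp(-0.1116 × 8/52.18) = 0.983, so entrants number about 55 × 0.8791 × 0.983 = 48 and 110 × 0.8569 × 0.983 = 93.

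**3. Mean planned open-label time.** Completers have 96 weeks; early switchers have 192 minus the switch week. The mean switch week is 8 + 52.18 × [1/k - 1.6865 × S/(1 - S)], where S is the completing fraction: 45.1 (placebo) and 47.8 (teriflunomide). Early switchers therefore average 146.9 and 144.2 weeks.
- Placebo/teriflunomide: 0.565 × 146.9 + 0.435 × 96 = 124.8 weeks.
- Teriflunomide/teriflunomide: 0.343 × 144.2 + 0.657 × 96 = 112.5 weeks.
- Ratio 1.11. Without double-blind dropout: 122.7 versus 111.0, also 1.11.

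**4. Expected crude percentages at equal true rates.** For a constant hazard h, average 1 - exp(-h × weeks/52.18) over individual exposure times, with no open-label discontinuation:

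| True rate | Placebo/terifl. | Terifl./terifl. |
|---|---|---|
| 0.3 per year | 50.4% | 47.0% |
| 0.1 per year | 21.1% | 19.3% |
| 10% risk per 96 weeks | 12.8% | 11.6% |
| 20% risk per 96 weeks | 25.0% | 22.9% |
| 40% risk per 96 weeks | 47.8% | 44.5% |
| 60% risk per 96 weeks | 68.3% | 64.8% |

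The largest excess is about 3.5 points. In the 20% row, the first-event rate is 12.1 per 100 patient-years in both groups, so a person-time rate removes the gap when the hazard is constant.

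**5. Compare with sampling error.** With 48 and 93 entrants, the standard error of a difference is about 6, 8 and 9 points in the 10%, 20% and 40% rows.

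**6. Sensitivity.**
- Open-label discontinuation of 20% per 2 years in both groups: 108.7 versus 99.4 weeks, ratio 1.09.
- Discontinuation of 31% (placebo/teriflunomide) versus 20%: exposure is equal.
- Relapse hazard ratio 0.8: exposure ratio 1.04. Hazard ratio 1: no imbalance.
- All risk in the first 24 open-label weeks, 10% in each group: crude percentages are equal, as they should be, but the rate per 100 patient-years is 4.6 versus 5.1, about 10% too low for placebo/teriflunomide.

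**The case against.** The strongest reply is that little depends on these columns. Safety is descriptive, the open-label data are uncontrolled and supportive, and crude percentages follow the protocol's own convention (Protocol 11.4.5). The expected shift is well below one standard error. Much of the clinically important ground already has a time-based analysis: the AESI list in SAP 2.1.4.1 has 17 categories, and discontinuation for any reason and liver elevations have Kaplan-Meier estimates. All of this stands, and it limits the point to a presentation improvement.

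The reply also says that a constant hazard is a poor description of this drug. Protocol 3.1.2.2 reports that in adults alopecia came mostly in the first 6 months and that nausea and diarrhea appeared early. Former placebo patients start teriflunomide for the first time in this period, so a higher early rate among them could be real. Every entrant has at least 96 planned open-label weeks, so early events are equally observable in both groups. This stands too. It also shows that a single rate per 100 patient-years is not a sufficient remedy, because it would distort early events in the opposite direction.

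What remains is that later or steadily accruing events in the general tables have no time-at-risk summary, and the expected distortion has a known direction.

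**Conclusion.** The point holds as a modest, inexpensive improvement to descriptive tables. It is not an error-rate problem. If events accrue at a roughly constant and equal rate, the placebo/teriflunomide percentages are expected to be higher by at most about 3.5 points.

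This rests on the planning relapse hazards, similar open-label discontinuation in both groups, every eligible patient entering the open-label period, and no switches for high MRI activity. The adverse event rates are illustrative assumptions, and the documents give no open-label exposure by former arm.

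A reader might infer more than this:
- *That the former placebo column will show more events.* Only a small expected excess follows, and sampling error exceeds it.
- *That all events are inflated.* Those confined to the first open-label weeks are not.
- *That the long-term safety table is biased in the same way.* SAP 2.4.5.1 analyses it as one overall group, so there is no arm comparison to inflate.
- *That nothing outside AESIs accounts for time.* Discontinuation and key laboratory findings do.

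**What to change.** In SAP 2.4.5.1, for the TEAE overview, common TEAEs, SAEs and TEAEs leading to discontinuation, by group:
1. Keep the crude number and percentage.
2. Add patient-years at risk and first-event incidence per 100 patient-years, with time at risk running to the first event or the end of the TEAE period.
3. Extend the interval at-risk method already specified for AESIs to the overview, SAE and discontinuation rows, so that early-onset events are not misread.

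The cost is a few extra columns or tables. Exposure is already derived, event onset dates are already in the planned listings, and the interval method is already written. The downside is that the single rate assumes a roughly constant hazard, so a footnote should direct the reader to the interval table.

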## **9.9 ACCELERATED ELIMINATION PROCESS**

Oral intake of cholestyramine or activated charcoal significantly accelerates the elimination of teriflunomide. The preferred washout medication is cholestyramine. Without using the accelerated elimination procedure, it may take years for teriflunomide plasma concentrations to reach acceptable low levels ( $\leq 0.02$   $\mu\text{g/mL}$ ) due to the long elimination half-life. All patients who complete or discontinue the study drug must undergo one of the accelerated elimination procedures described below. These procedures must be carried out at the study site by the Investigator. For patients who will continue to the commercially available drug, no accelerated elimination procedure is required.

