#### **10.1.4 Post drug elimination follow up visits**

Two post-washout follow up visits should be scheduled 2 weeks and 4 weeks after study medication discontinuation and initiation of the washout procedure. These visits are not required in case the patient receives commercial product immediately after the study end.

The following items will be checked/performed and recorded at Visit 21 (EOT+2W) and Visit 22 (EOT+4W):

- Adverse events reporting.
- Concomitant medications.
- Vital signs (BP, HR, body temperature and weight).
- Physical examination at EOT + 2 Weeks only.
- ECG should be performed only for patients who had new abnormalities on the EOT ECG.
- Clinical safety laboratories
  - Hematology and differential panel,
  - Liver function panel,
  - Pancreatic enzyme tests,
  - Uric acid and inorganic phosphorus.
- Post-washout PK sampling (note that the EOT+4W PK sample should be taken even if the EOT+2W PK sample is under 0.02 µg/mL, to document stability level as per EU SmPC).

In case of adverse events AE/abnormal laboratory values, or teriflunomide level > 0.02 µg/mL after the elimination treatment, follow up until resolution should be planned.

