2.1.4 Safety endpoints

The safety analysis will be based on the reported adverse events and other safety information, such as clinical laboratory data, vital signs, ECG, etc.

Observation period

The observation period of the open-label period will be divided into 3 epochs:

- The **treatment** epoch is defined as the time from the first administration of the IMP in the open-label period to the last administration of the IMP in the open-label period.
- The **accelerated elimination** epoch is defined as the time from 1 day after the open-label treatment epoch up to 4 weeks (28 days) after the last administration of the IMP in the open-label period or up to the first administration in optional additional extension period, whichever occurs first.

The treatment-emergent adverse event (TEAE) period will include both treatment and accelerated elimination epochs.

- The **posttreatment** epoch is defined as the period of time starting from the day after the end of the treatment-emergent adverse event period up to the end of the open-label period (defined as the first dose of optional additional extension IMP for patients enter optional additional extension period, or the last protocol-planned visit, EOT +4W, in the open-label period or the resolution/stabilization of a followed-up AE for patients do not enter).

The on-study observation period is defined as the combination of TEAE period and posttreatment epoch.

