2.3.3 Safety population

The safety population is defined as all patients enrolled in the open-label treatment period and received any dose of teriflunomide in the open-label period. It will be used for the safety analyses in the open-label period.

The safety analyses will be conducted according to the treatment patients actually received in the double-blind and open-label period (placebo/teriflunomide versus teriflunomide/teriflunomide) as well as the overall treatment group.

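### Adverse event percentages for the accelerated elimination epoch are divided by the whole safety population, including patients with little or no such epoch, so they are biased downward by an amount the documents do not fix

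*SAP*

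**What the plan says.** SAP 2.4.5.1 splits treatment-emergent events by epoch: "TEAEs during treatment epoch and TEAEs during accelerated elimination epoch will be analyzed separately and combined, as applicable". The same section gives one denominator for adverse event incidence tables: "The denominator for computation of percentages is the safety population within each treatment group". Protocol 11.4.5 has the same split and the same denominator for the double-blind period. Neither document gives an epoch-specific denominator.

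The open-label safety population is "all patients enrolled in the open-label treatment period and received any dose of teriflunomide in the open-label period" (SAP 2.3.3). SAP 2.1.4 defines the epoch as a calendar window: "the time from 1 day after the open-label treatment epoch up to 4 weeks (28 days) after the last administration of the IMP". Only a first dose in the extension shortens it. In the double-blind period the window is cut at inclusion in the open-label phase instead (Protocol 11.4.5). Taking cholestyramine or charcoal is not part of either definition.

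Protocol 9.9 makes washout the default: "All patients who complete or discontinue the study drug must undergo one of the accelerated elimination procedures described below". It then makes an exception: "For patients who will continue to the commercially available drug, no accelerated elimination procedure is required". On the two post-elimination visits, Protocol 10.1.4 adds: "These visits are not required in case the patient receives commercial product immediately after the study end".

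**The concern.** A separate table for this epoch is there to show what happens to children while the drug is being removed. Its percentages are informative only if the denominator is made up of patients who could be observed in that state. Under the stated rule two other groups stay in the denominator.

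- Patients who go directly into open label (double-blind report) or the optional extension (open-label report). Their window closes at the start of the next period, so they have almost no time in it.
- Patients who move to commercial teriflunomide. They are formally inside the 28-day window but are still on drug, have no elimination procedure, and need not attend either follow-up visit.

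The first group counts as event-free almost automatically. The second is only weakly observed, and any event it does report happened on teriflunomide rather than during washout. The posttreatment tables raise a similar question. In the open-label report that epoch starts after the 28-day window and, for patients not entering the extension, ends at the four-week visit or when a followed event resolves or stabilizes. Many patients will have almost no time in it.

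**Working it through.** The documents give no washout incidence, no share of patients entering washout and no dilution figure, so there is no planned number to reproduce.

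**Relation used.** Let f be the share of the safety population that washes out. If the others contribute no events, printed % = f × true %, and the understatement is 1/f. At f = 0.8, 0.5 and 0.2 a true 10% prints as 8%, 5% and 2% (1.25-, 2- and 5-fold).

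**Open-label report, by procedure.** Let d be the share who discontinue and do not resume teriflunomide, and c the share of completers who continue it. Then f = d + (1 − d)(1 − c). Neither d nor c is given for this period. Taking d = 20%, borrowed as an assumption from the double-blind sample size section:

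| c | f | 1/f |
|---|---|---|
| 0% | 1.00 | 1.0 |
| 25% | 0.80 | 1.25 |
| 50% | 0.60 | 1.67 |
| 75% | 0.40 | 2.5 |
| 90% | 0.28 | 3.6 |
| 100% | 0.20 | 5.0 |

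For f to fall below one half, c must exceed 0.5/0.8 = 62.5%. A 3-fold understatement needs c of at least 0.667/0.8 = 83%.

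**Open-label report, by the SAP's calendar window.** Only the optional extension cuts this window short, and it is for patients still under 18 at Week 192. 192 weeks is 3.68 years, so they must be under 18 − 3.68 = 14.32 years at randomization. Assume the planned 10% under 13 and ages uniform from 13 to 18. The eligible share is then 0.10 + 0.90 × 1.32/5 = 34%, so f is at least 0.66 and the dilution at most 1.5-fold. With 20% under 13 the ceiling is 1.7-fold. With ages uniform over 10 to 18 it is 1/(1 − 4.32/8) = 2.2-fold. These ceilings count commercial-drug patients as at risk.

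**Double-blind report.** Suppose everyone who relapses or completes enters open label. Washout then applies only to other discontinuers.

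- Flat planning figure of 20%: 1/0.20 = 5-fold.
- With relapse competing: hazards 0.4581 (placebo) and 0.2291 (teriflunomide) per year, discontinuation hazard −ln(0.8)/2 = 0.1116, T = 96 weeks = 1.84 years.
- Placebo: (0.1116/0.5697) × (1 − exp(−0.5697 × 1.84)) = 12.7%, or 7.9-fold.
- Teriflunomide: (0.1116/0.3407) × (1 − exp(−0.3407 × 1.84)) = 15.3%, or 6.5-fold.

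A true 20% in both arms would print as 0.127 × 20 = 2.5% on placebo and 0.153 × 20 = 3.1% on teriflunomide.

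**The case against.** A reader might infer that most patients never wash out and that washout harm is understated several-fold throughout. The documents do not support that for the open-label report. Protocol 9.9 sets the opposite default, the share exempted is not stated, and the optional extension is limited to young patients in France and possibly other countries. This part of the objection stands.

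The 5- to 8-fold figure belongs to the double-blind report, whose analysis has a separate SAP (SAP section 2) that was not available, so it rests on Protocol 11.4.5 alone. It also assumes full uptake. Open-label entry is optional and needs re-consent, and a confirmed relapse during the PK run-in does not trigger a switch. Any patient who declines and washes out raises f, so on these inputs 5- to 8-fold is an upper range. This stands too.

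Because the epoch is a calendar window, it would be wrong to say that patients on commercial drug cannot contribute an event. They can, so changing the denominator alone would leave the numerator mismatched. The relation printed % = f × true % is exact only if they report none.

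A reader might also infer a seriously distorted comparison between arms. The gap is 2.5% against 3.1% for the same true risk, with about 7 placebo patients (12.7% of 55) and 17 teriflunomide patients (15.3% of 110) in washout. That is slight.

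Finally, counts appear beside percentages and SAP 2.4.5 describes the safety analysis as descriptive with no systematic testing. This limits the consequences but does not answer the point. Readers of a descriptive table use the percentages, and no planned table shows how many patients entered the epoch.

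**Conclusion.** The point holds as a defect of the stated denominator. Patients with essentially no elimination epoch, or with no procedure and no required visits in it, are kept in the denominator of the epoch tables, and this pulls the washout percentages down. The exception would be commercial-drug patients reporting events at least as often as those washing out, which is unlikely without scheduled visits.

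For the open-label report the size cannot be determined: about 1- to 5-fold if 20% to 100% of patients wash out (assumed), and at most about 1.5- to 2.2-fold on the calendar definition under the assumed age distributions. For the double-blind report it would be about 5- to 8-fold, conditional on every relapsing or completing patient entering open label and on the double-blind SAP keeping the Protocol 11.4.5 rule. The combined treatment-emergent tables, which are the main safety presentation, are not affected.

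**What to change.** In SAP 2.4.5.1, and in the double-blind tables if they follow Protocol 11.4.5:

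- For the accelerated elimination tables, use as denominator the patients who stopped study drug and did not go directly on to further teriflunomide, and count events only in those same patients.
- Show events in patients continuing on commercial teriflunomide separately.
- For the posttreatment tables, use the patients with any follow-up in that epoch.
- Print the number entering each epoch.
- Keep the safety population for the on-treatment and combined tables.

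The SAP already applies this principle elsewhere: patients exposed at the start of each interval for events of special interest (2.4.5.1), and patients assessed for potentially clinically significant abnormalities (2.4.5). The change affects analysis only; no treatment or washout rule changes. The cost is one population flag, a short definition covering both numerator and denominator, and smaller denominators with less precise percentages.
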